## List of Abbreviations

### LIST OF ABBREVIATIONS

AE	Adverse Event/Adverse Experience
BE	Barrett's Esophagus
CFR	Code of Federal Regulations
Cox-2	Cyclooxygenase-2
CRF	Case Report Form
DSMB	Data and Safety Monitoring Board
EAC	Esophageal adenocarcinoma
FDA	Food and Drug Administration
FFA	Free fatty acid
GCP	Good Clinical Practice
GEJ	Gastroesophageal Junction
HGD	High grade Dysplasia
HIPAA	Health Insurance Portability and Accountability Act
IB	Investigator's Brochure
IL1 $\beta$	Interleukin-1 beta
IL6	Interleukin-6
IND	Investigational New Drug Application
IRB	Institutional Review Board
MetS	Metabolic syndrome
NSAIDs	Nonsteroidal anti-inflammatory drugs
$\omega$ 3 FFA	Omega 3 free fatty acid
PGE2	Prostaglandin E2
PHI	Protected Health Information
PI	Principal Investigator
SAE	Serious Adverse Event/Serious Adverse Experience
SOP	Standard Operating Procedure
SQ	Subcutaneous
TNF $\alpha$	Tumor necrosis factor-alpha

# 1 Introduction

Increased visceral abdominal fat is associated with increased risk of Barrett's esophagus (BE) and esophageal adenocarcinoma (EAC). Novel preliminary data gathered by us has revealed a reflux independent influence of visceral abdominal fat on esophageal pro-inflammatory and pro-neoplastic pathways, mediated via visceral fat produced saturated free fatty acids and activated macrophages.  $\omega$ 3 free fatty acids have been shown to inhibit epithelial PGE2 production by inhibiting COX-2 activity and modulating the macrophage phenotype from proinflammatory to anti-inflammatory. In this pilot randomized double blind placebo controlled study we wish to assess the ability of oral  $\omega$ 3 free fatty acids to downregulate pro-neoplastic and pro-inflammatory pathways in the esophagus. Pilot data from this proposal will enable us to design a larger adequately powered study assessing the role of  $\omega$ 3 free fatty acids as chemoprevention agents in subjects with BE, who are at substantial risk of developing EAC, a lethal cancer with rapidly rising incidence in the United States.

[figure not shown]
This document is a protocol for a human research study. This study will be carried out in accordance with the applicable United States government regulations and Mayo Clinic research policies and procedures.

## 1.1 Background

*BE and visceral abdominal fat:* Barrett's esophagus (BE) is characterized by intestinal metaplasia of the esophagus in response to esophageal injury and inflammation [1]. BE is the strongest risk factor and precursor of esophageal adenocarcinoma (EAC) a malignancy with rapidly rising incidence and poor outcomes. In addition to reflux, increased abdominal visceral fat has been identified as an independent risk factor for BE and EAC[2, 3]. Abdominal fat is composed of visceral and subcutaneous fat. Visceral fat may predispose to BE by mechanically increasing reflux and/or by reflux independent mechanisms [4]. We have found that increased visceral abdominal and gastroesophageal junction (GEJ) fat are independently associated with BE, esophageal inflammation and high grade dysplasia (HGD) [5]. Visceral fat is metabolically active, leading to a systemic inflammatory state and the metabolic syndrome. We have also identified Metabolic syndrome as a risk factor for BE, independent of reflux, in a population-based case control study [6], further supporting a reflux independent pathway by which visceral abdominal fat may modulate esophageal inflammation and neoplasia.

### *Visceral fat, Free Fatty Acids (FFAs) and Macrophage mediated inflammation:*

Abdominal visceral fat releases proinflammatory cytokines and saturated FFAs which are known to induce a systemic inflammatory insulin resistant state: which is strongly associated with BE [7, 8]. FFAs function as ligands modulating inflammatory responses, but with different effects. sFFAs exert proinflammatory, while  $\omega$ 3 FFAs exert anti-inflammatory effects [9-12]. sFFAs activate macrophages to a proinflammatory (M1) phenotype [13]. Preliminary data obtained by us show increased levels of serum sFFA in obese BE subjects compared

to controls, as well as higher density of activated macrophages (M1 phenotype) and their products in BE biopsies compared to controls. M1 macrophage produced proinflammatory cytokines (such as TNF $\alpha$ , IL6, IL1 $\beta$ ) are known to be overexpressed in BE and are thought to contribute to malignant progression to EAC in BE [14-16].

*Anti-inflammatory effects of  $\omega$ 3 FFA:* Increased intake of polyunsaturated FFAs and  $\omega$ 3 FFAs in particular, is associated with a 50% lower risk of BE [17].  $\omega$ 3 FFAs have been shown to have anti-neoplastic activity in the colon. *A major proposed mechanism by which  $\omega$ 3 FFAs exert anti-inflammatory and antineoplastic effect is by modulation of prostaglandin biosynthesis, by providing an alternate substrate for COX-2 (instead of the  $\omega$ 6 FFA : Arachidonic acid), which leads to decreased PGE2 production, epithelial proliferation and adenoma/aberrant crypt foci number in animal and human trials [9] [18-20]. We have shown in prior studies that increased levels of COX2 are seen with increasing grades of dysplasia in BE and that inhibition of COX-2 activity leads to reduced EAC incidence in an animal model of BE, by reducing PGE2 production [21, 22].  $\omega$ 3FFAs have also been shown to modulate macrophage phenotype from proinflammatory (M1) to anti-inflammatory (M2). GPR120 has been identified as a likely  $\omega$ 3FFA receptor, mediating the anti-inflammatory and insulin sensitizing effects of  $\omega$ 3FFAs on macrophages and tissue [13]. Our novel central hypothesis is that *oral supplementation with  $\omega$ 3 FFAs in obese BE subjects will lead to downregulation of pro-neoplastic inflammatory pathways in BE by modulating the esophageal macrophage phenotype from proinflammatory to anti-inflammatory.* We propose to test this hypothesis by the following specific aims, using a randomized controlled trial study design:*

Specific Aim 1: To estimate the magnitude and variation of changes in esophageal inflammation and injury in BE as measured by tissue PGE2 and the esophageal inflammation score, attributable to  $\omega$ 3 FFA supplementation.

Specific Aim 2: To estimate the magnitude and variation of changes in esophageal macrophage infiltration and modulation of esophageal macrophage phenotype attributable to  $\omega$ 3 FFA supplementation.

Specific Aim 3: To estimate the magnitude and variation in changes in esophageal mucosal impedance attributable to  $\omega$ 3 FFA supplementation.

Specific Aim 4: To define the baseline esophageal mucosal microbiome and the potential change in the esophageal mucosal microbiome attributable to  $\omega$ 3 FFA supplementation.

**Significance and Innovation:**

The prevalence of BE has been estimated to be 1.6-2.0% in the United States. The incidence of EA has increased exponentially in the Western world in parallel with the prevalence of obesity, now estimated to affect > 30% of the US population. *Radiofrequency ablation has emerged as an alternative modality to reduce the risk of progression to EAC in dysplastic BE, but is expensive, with potential endoscopic complications and a fairly high risk of recurrent IM (30% at 2 years) following successful ablation.* This study uses a safe compound ( $\omega$ 3 FFA) based on a novel biologically plausible, mechanistic hypothesis and strong supportive preliminary data to

[figure not shown]
attenuate and inhibit proinflammatory and pro-neoplastic pathways in subjects with BE who are at high risk of developing EAC, a lethal malignancy with rapidly increasing incidence. While used extensively in preclinical and clinical studies in the colon with encouraging results, there is no data on their ability to inhibit proinflammatory and neoplastic pathways in subjects with BE. If successful, this novel trial will lay the ground work for a larger adequately powered trial to demonstrate the use of  $\omega$ 3 FFA as a *novel chemoprevention compound* in subjects with BE to decrease EAC incidence. While inhibition of proinflammatory pathways in BE is possible with NSAIDs (and Aspirin), their use is associated with adverse effects including cerebrovascular and gastrointestinal bleeds even at low doses.  $\omega$ 3 FFA may provide a safer alternative to NSAIDs for chemoprevention in BE. Additionally, given the close association of obesity and esophageal injury,  $\omega$ 3 FFAs could also be used as an adjunct or alternative to proton pump inhibitors (PPIs) in modulating esophageal inflammation and injury, particularly in those patients with an incomplete response to PPIs. This can provide a novel alternative to PPIs in the management of patients with obesity and reflux induced esophageal injury, which is a very prevalent problem in the United States.

**Preliminary data:**

1. *Increased visceral and GE junction fat area are independently associated with BE, esophageal inflammation and HGD [5].* GE junction, visceral and subcutaneous (SQ) fat area were assessed in age and gender matched 50 BE cases and 50 controls, using CT scans. BE was strongly associated with visceral and GE junction fat area independent of BMI. There was no association with SQ fat area, suggesting a non-mechanical influence of visceral fat on BE pathogenesis. Furthermore, increased visceral fat area (but not SQ fat area) was also independently associated with severe esophageal inflammation and HGD, further suggesting a non-mechanical influence of visceral fat on esophageal inflammation and carcinogenesis.

2. *Metabolic Syndrome is a risk factor for BE independent of reflux[6].* We studied the association between BE and metabolic syndrome in a population based case control study: 309 subjects from Olmsted County, MN were studied (103 BE cases, 103 reflux + controls and 103 reflux - controls). 64% of cases, 49% of reflux + controls and 51% of reflux - controls had MetS. MetS was associated with a 2 fold increased risk of BE with reflux (+) controls (OR 1.9, 95% CI 1.1, 3.6, p=0.04) and reflux (-) controls (OR 1.9, 95% CI 1.1, 3.4 p=0.04) on multivariable regression analysis.

**Fig 1: Serum saturated and  $\omega$ 3 FFA (EPA) levels in BE subjects with and without central obesity**

[figure not shown]
3. *Centrally obese BE patients have higher serum sFFA levels and lower  $\omega$ 3 FFA levels than age, gender and BMI matched controls.* Fasting serum from 10 controls without BE and 20 age and gender matched BE cases was analyzed for serum FFA profiles, using mass spectroscopy. Patients with BE had higher saturated FFA and lower  $\omega$ 3 FFA levels than those without BE (figure 1).

[figure not shown]
4. *Central obesity increases risk of esophagitis and metaplasia.* In a population based screening study [23], 60 age, gender and reflux symptom stratified subjects were randomized to evaluation by sedated endoscopy, unsedated transnasal endoscopy or capsule endoscopy. 11 subjects with esophagitis or BE had higher waist circumference and waist hip ratios (measures of central obesity) than those without (table 1).

Variable, Mean (SEM)	BE or esophagitis (N=11)	No BE or esophagitis (N=47)
Waist circumference (cm)	100.3 (4.3)	95.8 (2.1)
Waist hip ratio	0.94 (0.02)	0.90 (0.01)
BMI	30.9 (1.7)	29.0 (0.8)

5. *Esophageal tissue PGE2 accurately reflects endoscopic and histologic esophageal injury.* Tissue esophageal PGE2 levels were measured in biopsies of 10 subjects with no symptoms of, endoscopic or histologic evidence of reflux and 10 subjects with esophagitis or BE. Levels in subjects with esophageal injury (mean 42 pg/mg) were significantly higher than those with no symptoms or signs of esophageal injury (mean 2 pg/mg),  $p=0.03$ . (Figure 2).

[figure not shown]

6. *BE patients have denser macrophage infiltration than controls.* IHC for CD68 and HAM56 (macrophage markers) was performed on esophageal biopsies from 5 BE cases (without endoscopic evidence of esophagitis) and 5 controls.[24] Mean counts of CD68 positive cells in BE were higher compared to controls ( $p=0.06$ ) (Figure 3).

7. *Sub-characterization of macrophages in BE: Increased M1 like macrophages in BE.* IHC using double labeling for CD68 and CD206 was performed on esophageal biopsies from subjects with BE [24]. Cells double labeling for CD68 and CD206 are M2 like cells and those labeling for only CD68 are M1 like cells. M2 like macrophages constituted a *minority* (30%) of all CD68 positive cells, indicating a preponderance of M1 like cells in BE tissue (Figure 4)

**Fig 4: Columnar metaplasia is associated with increased M1 like macrophage infiltration.** Immunofluorescence with double labeling for CD68 and CD206 on distal esophageal biopsies from subjects with BE.

[figure not shown]
8. *M1 Macrophage markers are more prevalent in BE compared to squamous tissue.* Esophageal biopsies were obtained from patients with and without BE on endoscopy and snap frozen at  $-80^{\circ}$  C. RNA was extracted from these biopsies using the RNAase easy kit. qPCR was performed for macrophage (CD68), M1 (MCP-1) and M2 (IL10, arginase) markers. Results show increased expression of CD68 RNA in BE tissue compared to that of normal squamous tissue ( $p=0.02$ ). MCP1, a M1 macrophage marker was also greater in BE tissue than

in squamous tissue ( $p=0.03$ ) (figure 5).

[figure not shown]
9. *Influence of saturated and  $\omega$ 3 FFA on macrophages in vitro.* THP-1 cell line, a human monocyte cell line was differentiated into macrophages using previously described methods [25]. Macrophages were treated with palmitic acid (PA), a saturated FA or docosahexanoic acid (DHA), a  $\omega$ 3 FFA, or both in combination. RNA was isolated using the RNAase easy kit (Qiagen). qPCR was then performed for macrophage (CD68), M1 (IL1 $\beta$ , MCP-1) and M2 (CD206, arginase) markers. Gene expression analysis was performed by calculating the  $\Delta C_t$  for each target gene using  $\beta$  actin as the reference gene. As seen in the results from figure 6a and 6b, exposure of macrophages to PA led to a proinflammatory response while administering DHA with PA lead to a substantial blunting of the proinflammatory response. Exposure to DHA led to the induction of M2 markers (CD206 and Arginase) in macrophages.

**Fig 5: Higher CD68 and MCP1 (M1 macrophage marker) mRNA in BE compared to squamous esophageal biopsies.**

qPCR for CD68 and MCP in squamous and BE biopsies.

**Fig 6A and 6B: Exposure of macrophages to satFFA leads to a proinflammatory response which is blunted by DHA (an  $\omega$ 3FFA) and induction of M2 macrophage markers.**

Hence in these preliminary data we have discovered increased visceral fat, serum saturated FFAs and M1 proinflammatory macrophage infiltration in BE and have found that exposure of macrophages to  $\omega$ 3FAs is able to blunt the proinflammatory and neoplastic cascade induced by saturated FFAs and induce a M2 phenotype. These data help support and justify our hypothesis of Specific Aims 1 & 2 and their feasibility.

## 2 Study Objectives

Specific Aim 1: To estimate the magnitude and variation of changes in esophageal inflammation and injury in BE as measured by tissue PGE2 and the esophageal inflammation score, attributable to  $\omega$ 3 FFA supplementation.

Specific Aim 2: To estimate the magnitude and variation of changes in esophageal macrophage infiltration and modulation of esophageal macrophage phenotype attributable to  $\omega$ 3 FFA supplementation.

Specific Aim 3: To estimate the magnitude and variation in changes in esophageal mucosal impedance attributable to  $\omega$ 3 FFA supplementation.

Specific Aim 4: To define the baseline esophageal mucosal microbiome and the potential change in the esophageal mucosal microbiome attributable to  $\omega$ 3 FFA supplementation.

## 3 Study Design

### 3.1 General Design

In this pilot randomized double blind placebo controlled study we wish to assess the ability of oral  $\omega$ 3 free fatty acids to downregulate pro-neoplastic and pro-inflammatory pathways in the esophagus. Pilot data from this proposal will enable us to design a larger adequately powered study assessing the role of  $\omega$ 3 free fatty acids as chemoprevention agents in subjects with BE, who are at substantial risk of developing EAC, a lethal cancer with rapidly rising incidence in the United States. Our plan is to complete the study on 80 participants, 40 in each group randomized to omega-3 or placebo. Subjects between 18-85 years of age, with known BE (no dysplasia and low-grade dysplasia) will be identified using an existing GI database for participation in this study. Invitation letters will be mailed to eligible subjects. Subjects meeting inclusion and exclusion criteria will be screened and consented. Once consent has been obtained baseline assessment and endoscopy with biopsy/brushings, and endoscopic mucosal impedance measurement will be completed. A single slice CT scan of the abdomen will also be obtained at baseline for each subject to quantify visceral and subcutaneous fat area in the abdomen. Subjects will then begin treatment and follow-up for the next 6 months. A final visit for evaluation and collection of tissue samples will be conducted at the end of the study. No risks of any particular seriousness or severity are anticipated. Blood and tissue samples will be obtained and used in this study as outlined in section 3.2. Any remaining samples will be stored in [name] -80C freezer located at Joseph M97 and used for future research in Barrett's esophagus.

Modulation of Esophageal Inflammation in Barrett's Esophagus by  $\omega$ 3 Fatty Acids

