#### 4.1 **Inclusion Criteria**

- Presence of BE defined as  $\geq 1$  cm of visible columnar mucosa in the distal esophagus with intestinal metaplasia on histology.
- Absence of high grade dysplasia or EAC on baseline histology.
- BMI  $> 30$  kg/m^2 (this has been shown to correlate strongly with increased abdominal visceral fat)[26] or Waist circumference  $> 102$  cm in men,  $> 88$  cm in women.
- Ability to give informed consent.

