#### 4.3 **Subject Recruitment, Enrollment and Screening**

Subjects between 18-85 years of age, with known BE (no dysplasia and low-grade dysplasia) will be identified using an existing GI database for participation in this study. Invitation letters will be mailed to eligible subjects. Subjects will be called to discuss study and scheduled for a screening visit. Subjects taking  $\omega$ 3 FFA as a supplement will discontinue use at least four weeks prior to visit 1. Subjects will report fasting 12 hours for this visit. Subjects meeting inclusion and exclusion criteria will be screened and consented. Baseline assessment will include the measurement of height, weight, waist circumference, hip circumference and waist/hip ratio using standard methods of anthropometric measurements. A comprehensive medication list will be obtained. Patients will also fill out the Reflux Symptom Questionnaire (RSQ)/GER Questionnaire a validated instrument to assess reflux symptoms All patients will continue their baseline PPI regimen to control gastroesophageal reflux. 20cc of blood will be drawn after 12 hours of fasting to obtain a baseline serum FFA profile . Clinical baseline blood will be drawn for inclusion/exclusion: INR, LDL, AST and ALT. Endoscopy will then be performed in a standard manner. Six biopsies will be obtained from the GE junction, and seven biopsies from the BE mucosa 1 cm above the GE junction. Two biopsies from each site will be formalin fixed and paraffin embedded (for inflammatory score assessment) and the remainder frozen at  $-80$  C for subsequent analysis. An additional seven biopsies will be obtained from the squamous mucosa at least 3 cm above the proximal end of the BE segment. Two will be placed in formalin (or other fixative) and paraffin embedded (IHC for macrophage cell counts) and the remainder will be snap frozen at  $-80^{\circ}$  C (PGE2 levels). Endoscopic brushings of the Barrett's segment as well as squamous tissue will be obtained and frozen for each subject. Endoscopic mucosal impedance measurement will be completed during endoscopy. A single slice CT scan of the

abdomen will also be obtained at baseline for each subject to quantify visceral and subcutaneous fat area in the abdomen.

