### **5.3 Method for Assigning Subjects to Treatment Groups**

A randomization schedule will be generated in the Division of Biomedical Statistics and Informatics and sent to the research pharmacy. Investigators and patients will be blinded to drug versus placebo assignment and only research pharmacy personnel and statisticians will have access to the assignments until the study is completed. Medications (drug and matching placebo) will be dispensed through the Mayo research pharmacy.

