## 7 Statistical Plan

### 7.1 Sample Size Determination

#### Statistical Analysis

Up to 90 patients with Barrett's will be identified and randomized to either drug or placebo. The primary analysis objective in this pilot study is to estimate response magnitude and variation which will be the information needed to design a larger adequately powered study to study the efficacy of  $\omega$ 3FFA as a chemoprevention agent in BE. The data will be summarized as mean, standard deviation, as well as median, and interquartile range, overall (baseline) and by treatment group (post-supplementation at 6 months). In addition, 95% confidence intervals for response mean (or median) treatment group values and 95% confidence intervals for treatment group differences in means (or medians) will also be calculated. Exploratory descriptive summaries of the response data will also be generated after stratifying on ASA intake.

Aim 1: The primary response outcome is tissue PGE2 levels and the main secondary response outcome is the histologic score of 3 or 4 (severe grades of inflammation). Other secondary outcomes include pre and post supplementation serum and tissue  $\omega$ 3 FFA levels.

Aim 2: The primary response outcome is the Cytokine expression profile in esophageal biopsies as measured by qPCR [IL1 $\beta$ , IL6 (M1 markers) versus IL1, IL10 (M2 markers)]. Secondary response outcomes include change in esophageal macrophage counts and phenotype proportions (total, %M1, %M2).

Aim 3: The esophageal mucosal impedance of the squamous epithelium and columnar epithelium will be summarized as mean (SD) or median (IQR) depending on data normality. The data will be summarized (baseline and post-supplementation) by treatment group. Change in impedance (Baseline – post supplementation) will be compared using appropriate statistical tests. Secondary outcome analysis will include testing the association between esophageal mucosal impedance and measures of central obesity (including waist circumference, waist hip ratio and abdominal visceral fat area on CT scan).

Aim 4:

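### Dysplasia grade is available at baseline and plausibly related to PGE2, but the PGE2 contrast does not use it; this may cost some precision and blur the pilot SD, without biasing the estimate

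*Combined protocol and SAP*

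**What the plan says.** **Population.** Section 3.1 states that subjects "with known BE (no dysplasia and low-grade dysplasia) will be identified using an existing GI database for participation in this study"; sections 4 and 4.3 repeat this. The upper limit on grade is set in section 4.1: "Absence of high grade dysplasia or EAC on baseline histology". Two grades therefore remain, none and low.

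**Biology.** Section 1.1 reports from the investigators' own work that "increased levels of COX2 are seen with increasing grades of dysplasia in BE". It adds that, in an animal model, inhibiting COX-2 lowered cancer incidence through reduced PGE2 production.

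**Outcome and analysis.** Section 7.1 says of Aim 1: "The primary response outcome is tissue PGE2 levels". The arms are summarized at six months, and "95% confidence intervals for treatment group differences in means (or medians) will also be calculated". No covariate is named. The only factors singled out for stratified summaries are aspirin and NSAID use.

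**Allocation.** Section 5.3 says: "A randomization schedule will be generated in the Division of Biomedical Statistics and Informatics and sent to the research pharmacy". Sections 4.3 and 5.6 add nothing about strata. The planned size in section 3.1 is given as: "Our plan is to complete the study on 80 participants, 40 in each group randomized to omega-3 or placebo".

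**Tissue.** Section 3.2 assays PGE2 in esophageal biopsies without naming a site. Section 4.3 says: "An additional seven biopsies will be obtained from the squamous mucosa at least 3 cm above the proximal end of the BE segment". The frozen part of that squamous set is the only one labelled for PGE2. The frozen gastroesophageal junction and Barrett's biopsies are kept for later, unspecified analysis.

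**The concern.** The protocol itself supplies a reason to expect grade to matter for PGE2, and grade should be in hand. It defines the database search, and baseline histology has to be read to apply the eligibility criteria. The plan already applies this reasoning to aspirin and NSAID use because of their effect on PGE2, but it is silent on grade.

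The pilot's stated product is the magnitude and variation of response, for use in designing a larger trial. If grade is related to PGE2 in the assayed tissue, leaving it out has two consequences:

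- The interval for the arm difference is wider than it need be.
- The reported SD combines within-grade and between-grade spread, with no way to separate them. The designers of the next trial could then not plan an adjusted analysis or a different mix of grades from it.

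**Working it through.** Section 7.1 gives no effect size, SD or power for PGE2, so there is no planned figure to reproduce. The only PGE2 values in the documents are the means in the preliminary data, 42 and 2 pg/mg. They compare injured with uninjured esophagus, not dysplasia grades, and carry no SD.

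**Inputs**
- From section 3.1: 40 completers per arm.
- Assumed: low-grade share p = 0.10 to 0.25 (8 to 20 of 80).
- Assumed: grade effect d = 0.5 to 1.5 within-grade SD.
- Assumed: within-grade correlation r between baseline and six-month PGE2 of 0.5 or 0.7, with a grade effect that is stable over time.

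The within-grade SD is set to 1, and v = p(1 − p)d² is the between-grade variance.

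**Step 1: unadjusted contrast.** The share of outcome variance due to grade is v/(1 + v).

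| p | d | v | share due to grade |
|---|---|---|---|
| 0.10 | 0.5 | 0.0225 | 2.2% |
| 0.20 | 1.0 | 0.16 | 13.8% |
| 0.25 | 1.5 | 0.4219 | 29.7% |

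In the middle case the pooled SD is √1.16 = 1.077 within-grade SD. The gain from adjustment is worth 80/(1 − 0.138) = 92.8, or about 13 more completers.

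**Step 2: standard errors in the middle case.**
- Adjusted for grade: √(2/40) = 0.224.
- Unadjusted: 0.224 × 1.077 = 0.241.

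**Step 3: chance imbalance.** With 8, 12, 16 or 20 low-grade subjects split at random 40:40, the arms differ by at least 10 percentage points in low-grade share with probability 0.263, 0.348, 0.402 or 0.439. At d = 1, ten points move the difference by 0.10 SD, against a 95% half-width of 1.96 × 0.224 = 0.44 SD.

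This is not a second harm on top of Step 2. The SD of the shift at p = 0.20 and d = 1 is √(2 × 0.16/40) = 0.089, and 0.224² + 0.089² = 0.050 + 0.008 = 0.058 = 0.241². The unadjusted standard error already contains it.

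**Step 4: with baseline PGE2 in the model.**
- Residual variance with baseline alone: (1 + v) − (r + v)²/(1 + v).
- Residual variance with baseline and grade: 1 − r².
- Proportion that grade then removes: v(1 − r)/(1 + r + 2v).

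At p = 0.20 and d = 1:
- r = 0.5: 0.08/1.82 = 4.4%, about 4 completers (80/0.956 = 83.7).
- r = 0.7: 0.048/2.02 = 2.4%, about 2 completers (80/0.976 = 82.0).

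At the extreme corner (p = 0.25, d = 1.5) with r = 0.5: 0.2109/2.3438 = 9.0%, down from 29.7%.

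**The case against.** The strongest objection is about tissue. Section 4.3 labels only squamous biopsies, taken outside the Barrett's segment, for PGE2, whereas the COX-2 gradient is reported within Barrett's mucosa. Nothing in the documents says that grade inside the segment predicts PGE2 above it. This stands, and it makes the point conditional. It does not remove the point: Aim 1 concerns injury in Barrett's esophagus, section 3.2 leaves the site open, and Barrett's biopsies are also frozen.

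Second, a link between grade and PGE2 is inferred. Section 1.1 reports COX-2 by grade, not PGE2, and gives no figure for the single step from no dysplasia to low grade. This also stands, and it is why the size rests on assumed ranges.

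Third, PGE2 is measured at baseline and the aims speak of changes, so a change score or baseline adjustment would absorb most of a stable grade difference. That is correct, as Step 4 shows. But section 7.1 specifies neither for PGE2: it summarizes baseline overall and the arms only after supplementation.

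A reader might infer more than the documents support:

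- **That an excess of low-grade subjects in one arm would bias the result.** Under randomization it is random error and already inside the planned 95% interval.
- **That the schedule is known to be unstratified.** The documents do not describe its structure; they only name no stratum.
- **That the within-grade SD should replace the pooled SD for planning.** That would understate the size of a later trial with the same mix and an unadjusted analysis.
- **That the qPCR markers need the same covariate.** The stated gradient concerns COX-2 only.

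**Conclusion.** The point holds as a cheap improvement to an estimation pilot. Two grades are enrolled, the protocol gives a plausible reason why grade could relate to PGE2, and no allocation or analysis text uses it. The consequence is some lost precision and a mixed SD, to the extent that PGE2 in the assayed tissue differs by grade.

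The documents cannot fix the size. Over the assumed ranges, the gain in an unadjusted contrast runs from negligible (about 2% of variance) to substantial (about 30%), and the upper end needs both assumptions at their extreme. Once baseline PGE2 is in the model, a central case gives only about 2-4%. Most of the benefit therefore comes from baseline adjustment, and grade adds a smaller amount at little cost.

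**What to change.** In section 7.1:

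1. Prespecify the arm contrast for tissue PGE2 as a model with baseline PGE2 and dysplasia grade (none or low, from baseline histology) as covariates.
2. State which biopsy site supplies the PGE2 assay, and reconcile sections 3.2 and 4.3 accordingly.
3. Report both the pooled SD and the grade-adjusted residual SD, together with the PGE2 mean and SD by grade, so that a later trial can plan for either form of analysis.

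The cost is SAP wording and one degree of freedom for grade. The low-grade group may be very small (a 10% share would be about 4 per arm), so no separate effect should be claimed in it.

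Stratifying the schedule by the grade held in the database is optional, and only worth doing if the schedule has not been issued. The Schedule of Events puts endoscopy and randomization both at Month 0, so baseline histology may not be read in time for allocation.
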